- Renal consult

6) Provider awareness outcomes

- Chart documentation of AKI (by post-discharge ICD-10 codes)
- Chart documentation of AKI (adjudicated)

Study Procedures

Randomization

Randomization will occur the moment AKI is detected by the electronic monitoring system within the EPIC best practice alert framework, as developed by JDAT. Beyond the primary intervention, no further tests or procedures will be performed on subjects in this trial. Randomization will be performed within the Epic system using a random number rule that is incorporated in the alert. This ensures that, upon meeting criteria, each patient is immediately and randomly assigned to an arm. Logic checks within the alerts ensure that once a patient is assigned to an arm, they remain on that arm for the remainder of their hospital stay.

Fourteen days post-randomization

Primary endpoint ascertainment

Thirty days post-randomization

Secondary endpoint ascertainment

Statistical Plan

Sample Size Determination

:

In our retrospective analysis of patients with AKI at 3 potential study hospitals, the composite outcome of death, dialysis, and progression of AKI was 24.5% (of 29,027 individuals with AKI). We believe a clinically meaningful relative reduction in this risk would be 20%, leading to an absolute rate of 19.6% in the intervention group. By enrolling 5,024 patients (2,512 in each group), we would have 90% power to detect a difference in outcome at least this extreme at a two-sided alpha of 0.05 as calculated using the Cochran-Mantel-Haenszel test (accounting for 6 hospital strata). We have elected to increase this number by 20% to account for potential contamination of the effect across

study arms, leading to a final sample size of 6,030 individuals. This sample size will also allow us to detect at least a 16% increase in best practices measures in the intervention group.

We must also consider that patients enrolled once in the trial will be excluded from enrolling again (on another admission, for example). While we don't have data on the rates of recurrent AKI we estimate that up to 20% of eligible patients may be excluded on this basis, which may slow recruitment somewhat.

In addition, pauses in trial enrollment may occur due to protocol changes / amendments based on feedback from providers and for quality improvement activities.

As such, we expect active enrollment, data acquisition, and outcome assessment to be completed over a three-year period.

Statistical Methods

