The primary analysis will utilize the intention to treat principle. The primary outcome (a composite of progression of AKI, dialysis, and death) will be compared across the groups using the Mantel-Haenszel chi-square test for correction for the 6 study strata (by hospital). Statistical significance will be based on a p-value of <0.05.

In addition, a retrospective examination will be performed to assess improvement in the control group before / after intervention as a measurement of contamination. We expect that providers who receive AKI alerts on some patients may be more likely to look for AKI in other patients, potentially diluting the effect of the intervention – this pre/post intervention analysis will help in assessing that level of contamination.

Because we are enrolling patients across six sites, we will do an exploratory analysis to determine the efficacy of alerts independently at each hospital.

We have specified several subgroups in whom the benefit of an AKI alert may differ from the general population. These groups will be analyzed as secondary and exploratory analyses. They include:

- Surgical patients
- Subjects with baseline creatinine <1.0mg/dl
- Subjects with baseline creatinine <0.5 mg/dl
- Females (due to lower rate of increase in creatinine after AKI)
- African Americans (due to higher rate of increase in creatinine after AKI)
- Elderly subjects (age > 65, age > 70, and age > 75)
- Subjects in an ICU at the time of the alert
- Subjects who enter the study based on relative vs. absolute creatinine criteria vs. both

Finally, as the academic year progresses, new clinicians (such as residents and interns) may become more facile in their ability to recognize AKI, which may attenuate the effect of this intervention. We will model this in exploratory analyses using an intervention-by-time of year interaction term in models of the primary outcome.

4. Genetic Testing N/A

A. Describe

- i. the types of future research to be conducted using the materials, specifying if immortalization of cell lines, whole exome or genome sequencing, genome wide association studies, or animal studies are planned
 - ii. the plan for the collection of material or the conditions under which material will be received
 - iii. the types of information about the donor/individual contributors that will be entered into a database
 - iv. the methods to uphold confidentiality

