12. **Statistical Considerations:** Describe the statistical analyses that support the study design.

Statistical Methods

The primary analysis will utilize the intention to treat principle. The primary outcome (a composite of progression of AKI, dialysis, and death) will be compared across the groups using the Mantel-Haenszel chi-square test for correction for the 6 study strata (by hospital). Statistical significance will be based on a p-value of <0.05 .

In addition, a retrospective examination will be performed to assess improvement in the control group before / after intervention as a measurement of contamination. We expect that providers who receive AKI alerts on some patients may be more likely to look for AKI in other patients, potentially diluting the effect of the intervention – this pre/post intervention analysis will help in assessing that level of contamination.

We have specified several subgroups in whom the benefit of an AKI alert may differ from the general population. These groups will be analyzed as secondary and exploratory analyses. They include:

- Surgical patients
- Subjects with baseline creatinine <1.0 mg/dl
- Subjects with baseline creatinine <0.5 mg/dl
- Females (due to lower rate of increase in creatinine after AKI)
- African Americans (due to higher rate of increase in creatinine after AKI)
- Elderly subjects (age > 65 , age > 70 , and age > 75)
- Subjects in an ICU at the time of the alert
- Subjects who enter the study based on relative vs. absolute creatinine criteria vs. both

Finally, as the academic year progresses, new clinicians (such as residents and interns) may become more facile in their ability to recognize AKI, which may attenuate the effect of this intervention. We will model this in exploratory analyses using an intervention-by-time of year interaction term in models of the primary outcome.

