Due to the unexpected finding of increased harm from the alert at non-teaching hospitals, we conducted several *post hoc* analyses, which are specifically identified in the results. To determine if the effect was mediated by actions downstream of the alert, we performed a formal mediation analysis using the method of Baron and Kenny (adjusted for age, sex, race, creatinine, blood urea nitrogen, white blood cell count, heart rate, respiratory rate, systolic and diastolic blood pressure, CHF, hypertension, diabetes, malignancy, modified SOFA score and Elixhauser comorbidity score at the time of randomization) of the following hypothesized mediators: markers of fluid overload, certain medications, the presence of renal consult, attending involvement in the care of the patient (as measured by the percent of alerts that went to attendings versus other providers), and the burden of other interruptive alerts (such as those for sepsis or medication interactions).^{5,6} The burden of other interruptive alerts was quantified as the number of other alerts received while the patient was eligible to be receiving AKI or Control alerts, divided by the amount of time they were eligible, leading to an average “non-aki alert per day” metric. Finally, we examined the rates of death and AKI progression in the time period 2 years prior to the start of the trial in each hospital to assess the degree of contamination across the study arms.

We assessed whether alert effectiveness changed over time by including an interaction term representing “time from first enrollment at this hospital” with the randomization status in a logistic regression equation. A significant p-value for this interaction term would suggest that the effect of the alert waxed or waned over time once it was “live” at a given hospital.

Our preliminary data suggested that 24.5% of patients would experience the composite outcome. We determined that a relative 20% reduction in this outcome (to 19.6) would be clinically significant. A sample size of 2,512 in each arm of the study achieves 90% power to detect this degree of change, but given the potential for contamination across study arms (whereby clinicians “learn” to identify and care for AKI over the course of the trial), which would tend to bias the results towards the null, we inflated the sample size by 20% to a total of 6,030.

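### The SAP's alert-by-time analysis measures drift since go-live; the protocol's planned alert-by-time-of-year interaction is not described, and the SAP term is a poor substitute for it

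*SAP*

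**What the plan says.** The protocol gives a mechanism and a model. Under Statistical Methods (section 3, repeated in section 12, Statistical Considerations) it expects that "as the academic year progresses, new clinicians (such as residents and interns) may become more facile in their ability to recognize AKI", with a possible weakening of the alert's effect. It then commits to a test: "We will model this in exploratory analyses using an intervention-by-time of year interaction term in models of the primary outcome". It does not limit that term to particular hospitals.

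The SAP (Statistical Analysis) describes one analysis of effect over time: "We assessed whether alert effectiveness changed over time by including an interaction term representing" the "time from first enrollment at this hospital". The model is a logistic regression in which randomization status interacts with that clock. A significant result, the SAP says, "would suggest that the effect of the alert waxed or waned over time once it was" live at a given hospital. No time-of-year or academic-year term is described, and the SAP does not say that the planned term was replaced or why.

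On duration, the protocol (Sample Size Determination) states: "we expect active enrollment, data acquisition, and outcome assessment to be completed over a three-year period". Neither document gives enrolment dates.

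**The concern.** The two time variables answer different questions. Time since first enrolment picks up alert fatigue, or learning, after the alert goes live. Time of year picks up the trainee cycle that the protocol named. The two coincide only when enrolment lasts a single year and starts with the academic year.

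Trainee presence also matters for interpreting this trial: the SAP reports that grouping hospitals into teaching and non-teaching accounted for the differing alert effects. A planned question about trainee experience is therefore worth answering, and the SAP as written does not show that it was.

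**Working it through.** The documents give no power or threshold for a time interaction, so there is no figure of theirs to reproduce. Two checks show how far the SAP's variable can stand in for the protocol's.

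**Inputs from the documents**
- Control risk 24.5% (SAP, Statistical Analysis).
- Enrolment from SAP Box 1: 2,515 + 1,248 + 935 + 503 = 5,201 at teaching hospitals 1-4, and 684 + 146 = 830 at non-teaching hospitals 5-6; total 6,031.
- Design effect 24.5% to 19.6%: log odds ratio = ln[(0.196/0.804)/(0.245/0.755)] = -0.286.

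**Assumptions (not in the documents)**
- Equal arms, uniform enrolment over 24, 30 or 36 months, a common go-live month (all 12 tried), and a linear time term.
- The alert's log odds ratio starts at -0.5 (or -0.286) at the beginning of each academic year, falls linearly to 0 by its end, and fully resets. It is 0 throughout at hospitals 5-6.
- Two-sided Wald test at 0.05.

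**Check 1: overlap of the two clocks.** Let t be years since first enrolment over n whole years, φ the fraction of the academic year already elapsed at go-live, and s = (t + φ) mod 1. Then Cov(t, s) = 1/12 - φ(1 - φ)/2, SD(t) = n/√12 and SD(s) = 1/√12, so

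r = [1 - 6φ(1 - φ)]/n.

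- Start aligned with the academic year (φ = 0): r = 0.50 for n = 2 and 0.33 for n = 3.
- Mid-year start (φ = 0.5): r = -0.25 for n = 2 and -0.17 for n = 3.
- r is negative when φ lies between (1 - √(1/3))/2 = 0.21 and 0.79, roughly 2.5 to 9.5 months into the academic year. A yearly fading would then appear on the SAP clock as a slight strengthening.

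**Check 2: power.** For the academic-month term over whole years,

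SE² = [1/(p0q0) + 1/(p1q1)] / [(N/2)(1/12)], z = slope/SE.

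Hospitals 1-4, start -0.5: the mean log odds ratio is -0.25, so p1 = 0.2017. SE² = (5.406 + 6.210)/(5,201/24) = 0.0536, SE = 0.2315, z = 0.5/0.2315 = 2.16, power about 58%.

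The full calculation fits each logistic model to expected data. In all hospitals over whole years the academic-month term gives z = 1.97, power about 50%. The SAP term's z is close to r times this:
- 24 months, aligned start: 0.50 × 1.97 = 0.99, power about 17%.
- 24 months, mid-year start: -0.25 × 1.97 = -0.49, power about 8%, wrong sign.
- 36 months, aligned start: 0.33 × 1.97 = 0.66, power about 10%.

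Ranges over 24, 30 and 36 months and all 12 start months:

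| Start-of-year log odds ratio | SAP term, all hospitals | Academic-month term, all hospitals | Academic-month term, hospitals 1-4 |
|---|---|---|---|
| -0.5 | 5-17% | 44-56% | 51-64% |
| -0.286 | 5-9% | 19-24% | 21-27% |

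**The case against.** Several points on the other side stand.

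- **The yearly reset is an assumption.** The protocol says that clinicians improve during the year, not that the effect is fully restored at each intake. If only half of it is restored, under the -0.5 assumptions, the academic-month term in hospitals 1-4 has about 16-36% power and the SAP term about 5-31%, so the ranges overlap.
- **The larger effect is generous.** A log odds ratio of -0.5 takes 24.5% to 16.4%, a 33% relative reduction against the 20% design target. With a design-sized start the planned term would itself usually be null.
- **The calendar is unknown.** The three years are a forecast that includes data acquisition and outcome assessment, and go-live dates may differ by hospital.
- **Limiting the model to hospitals 1-4 is a new analysis.** The protocol's term covers all hospitals, and the teaching/non-teaching grouping followed from observed results. Hospitals 5-6 hold only 830 of 6,031 patients (13.8%).

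A reader might go further and infer that the SAP term cannot detect a yearly pattern, that the academic-year question was never tested, or that the SAP offers a null result as its answer. The documents support none of these. The SAP term picks up part of a cycle when enrolment starts with the academic year. The SAP is a past-tense methods account that does not list every exploratory analysis, so they show only that the term is not described. And the SAP confines its reading to change since go-live and interprets only a significant result.

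None of this closes the gap between the planned analysis and the one described.

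**Conclusion.** The point holds as a discrepancy worth correcting. The protocol commits, in two places, to an exploratory arm-by-time-of-year interaction; the SAP describes a different time interaction and gives no explanation. If enrolment spans more than one academic year, the SAP term is a weak and possibly wrong-signed proxy.

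The difference in kind follows from the definitions of the two variables. The size of the power gap rests on the assumed yearly pattern, full reset, uniform enrolment and linear term, and it narrows if the reset is partial or the effect smaller. The primary test and the secondary outcomes are untouched.

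**What to change.** In the SAP's Statistical Analysis section:

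1. Add the protocol's arm-by-time-of-year interaction for the primary outcome in all hospitals, for example with months since the start of the academic year as the time variable. Keep the existing time-since-first-enrolment interaction beside it.
2. Report both with 95% confidence intervals, as exploratory.
3. Report a version limited to teaching hospitals 1-4, where the trainee mechanism applies, as an additional analysis labelled as not in the protocol.
4. State that the time-since-first-enrolment term does not test the academic-year hypothesis.

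The cost is one or two extra exploratory models of limited power, using randomization dates already held. A null result from them should not be read as evidence that the effect is constant over the academic year.
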